4.2 Study Population

Hospitalized adult patients with suspected or confirmed pneumonia at time of admission or while admitted to the ED who are prescribed antibiotics (including septic patients with respiratory focus).

Studies show that PCT is not affected by certain cancers so those patients will be included. Several studies have shown that PCT is a promising and reliable infection marker in patients with cancer^{30,31}. Neuroendocrine tumors and the presence of metastases have been linked to false positive PCT values^{32,33}. Thus, metastatic cancer, liquid tumors, neuroendocrine tumors and unstable patients who are on check point inhibitors or experiencing mucositis (e.g. mouth lesions or intestinal bleeds) will not be included.

4.2.1 Inclusion Criteria

- Hospitalized adult patients ≥ 18 years of age

- Suspected or confirmed LRTI pneumonia <28 days at time of admission to the hospital (ED) who are prescribed antibiotics.
- Minimum of 2 (two) blood samples available for PCT value assessment between 6 and 48 hours apart.

4.2.2 Exclusion Criteria

- Patient has tested positive for SARS-CoV-2
- Patients who are not admitted to the hospital
- Patients admitted to home health
- Major surgeries, defined as any procedure in which an incision is made with the exception of superficial procedures (eyes, cornea, skin, dental procedures), organs removed, or normal anatomy altered (e.g. open thoracic, abdominal and/or major orthopedic surgery), in the past 1 month or expected surgical procedure or patient receiving antibiotics for surgical prophylaxis
- Known Pregnancy
- Primary and acquired cell-mediated immune deficiency (HIV with CD4 <350 cells/mm³; with receipt of systemic chemotherapy and/or biologics in the past 3 months for reasons other than malignancy)
- Active metastatic cancer or neuroendocrine tumor or liquid tumor and/or on check point inhibitors within 3 months or has signs of mucositis (e.g. mouth lesions or intestinal bleeding).
- Neutropenia (<1,500 ANC)
- Patients with cystic fibrosis
- Infection where long courses of antibiotics are the standard of care (more than 2 weeks) other than for anti-inflammatory reasons
- Concomitant non-pulmonary bacterial infection that requires antibiotic therapy based on an active medical team decision.
- Antibiotics given for non-infectious indications (e.g. rifaximin for hepatic encephalopathy)
- Patients receiving dialysis
- Patients with solid organ transplant, bone marrow transplant or stem cell transplant recipient
- ST elevation myocardial infarction
- Prior enrollment into this study within 30 days
- Patient experiencing major trauma defined as any injury that could cause prolonged disability and/or an Injury Severity Score >15, and/or burns or patient under extracorporeal circulation confirmed by a second research staff member.
- Patient with acute viral hepatitis and/or decompensated severe liver cirrhosis (Child-Pugh Class C).
- Patient with prolonged or severe cardiogenic shock defined as decreased cardiac output leading to end organ injury (e.g. severe hypotension or AKI or oliguria or altered mental status or cool extremities or respiratory distress AND evidence of metabolic acidosis on lab testing).
- Patient with pancreatitis, chemical pneumonitis or heat stroke
- Active infection with invasive fungal pathogen (e.g. candidiasis, aspergillosis) or plasmodium falciparum malaria or mycobacteria

- Patient under treatment with OKT3 antibodies, OK-432, interleukins, TNF-alpha and other drugs stimulating the release of pro-inflammatory cytokines or resulting in anaphylaxis.
- Patient is under hospice care
- Patient with ventilator-associated pneumonia
- Patients with untreated, active, and symptomatic autoimmune disease
- Patients actively enrolled in other clinical trial involving immunomodulatory therapy.
- Patient with empyema, abscess, or cavitary/necrotizing pneumonia

4.2.3 Definition of suspected or confirmed LRTI

- Pneumonia requires one respiratory symptom plus one finding during auscultation or one sign of infection evidenced by core temperature of 38C, shivering, or a leukocyte count greater than 12,000u/ μ L or less than 4,000u/ μ L independent of antibiotic pretreatment.
- **pneumonia** will be defined as a new infiltrate on chest radiograph as defined by the IDSA/ATS 2007 CAP Guidelines.

4.2.4 Definition of treatment or readmission for CDI

- Treatment for CDI which consists of oral vancomycin, fidaxomicin, or oral or IV metronidazole or fecal microbiota transplantation
- Hospital re-admission within 30 days after enrollment coded for a primary diagnosis of CDI using ICD-10

4.2.5 Definition 'until day 30'

Day 30 is defined as the thirtieth calendar day after ED or hospital admission.

4.2.6 Monthly patient report

A report with the names and dates of birth of all Mass General Brigham enrolled patients will be created in REDCap every month. This report will be checked to make sure there are no duplicate patients enrolled at different sites within 30 days of the patient's original enrollment.

4.2.7 Cross checking charts

Information entered in REDCap by research staff will be subject to detailed cross check by one of the other unblinded study coordinators. Select study coordinators will be checking information from another site using EPIC.

Information to be cross-checked includes:

- Admission date
- Discharge Date
- PCT values
- Composite adverse events
- Antibiotics names (enrollment and daily)
- Antibiotics doses

Discharge antibiotics names
Discharge antibiotics doses
Discharge antibiotics duration
Survival at day 30

In the case of errors in 3 different sections and/or a 15% error of all values, all information related to the enrolled subject will be cross-checked by the study coordinator.

5 BLOOD SAMPLING

5.1 Collection of specimen

Left over serum from daily routine sampling will be collected in every study patient (intervention and control) and PCT will be measured. Samples should be processed according to clinics' standard operating procedures to gain serum.

5.2 Handling of specimen and labeling of PCT measurements

All sample processing should occur at room temperature (RT) at the time points specified in section 4.1. Samples should be processed according to the Elecsys B·R·A·H·M·S PCT™ or Abbott Alinity package insert, depending on site.

All samples will be coded in the eCRF using a unique study identifier.

6 RANDOMIZATION AND MEASUREMENT OF PROCALCITONIN

6.1 Randomization

Admitted patients will be screened, and eligible patients will be randomly assigned in a 1:1 ratio to the (i) PCT algorithm + stewardship team arm or (ii) the standard care arm.

6.2 Procalcitonin (PCT) Measurement

Procalcitonin will be measured with the Elecsys B·R·A·H·M·S PCT™ assay or Abbott Alinity and site personnel will be responsible for PCT measurements according to standard hospital procedure.

PCT results will be unblinded in the PCT arm (i.e. antibiotic management guided by the PCT algorithm + stewardship team) and blinded in the control arm (i.e. antibiotic management guided by standard of care). Research staff will enter PCT results in the eCRF (REDCap) and also ensure that the stewardship team views the results and makes a recommendation for PCT arm patients at the time frames specified in section 4.1.

Every site will have an SOP or delegation log with all key personnel listed including the core lab director/manager who will have confirmed that their site has PCT testing validated and ready for use.

If during the hospital course, patients meet an enrollment ineligibility criterion (e.g., developed a non-pulmonary infection, had to undergo a major surgery...), PCT levels will stop being measured and no further intervention from the stewardship team will be made. However, patients will continue to be monitored.

7 STUDY DATA

Data from the participating patients will be collected in electronic Case Report Forms (“CRF”) (see 9.4 Case Report Form). These clinical parameters will be collected to determine the clinical status of the patients.

7.1 Clinical Data Collection

The following clinical parameters will be collected in the corresponding eCRFs:

- **Socio-demographics at baseline PCT measurement D0 only** (age, gender, race, weight)
- **Hospitalization Details** (Enrollment date, time, number of days in the ICU, number of days in the general ward, number of mechanical ventilation days; admission date, time, diagnosis; discharge date, time diagnosis; ICU admission, date, time, reason for ICU and hospital admission)
- **Medical History** (history of present illness, list of chronic conditions)
- **Clinical Assessment** (date, time, physical exam, chief complaint, suspected site of infection, PSI, CURB 65 score)

- **Vital Signs at rest** (heart rate, respiratory rate, blood pressure, SpO₂)
- **Imaging Results for each image ordered while enrolled** (Chest radiograph, Chest CT: Date, time, results summary)
- **Laboratory Values included in the standard care of a patient hospitalized with suspected infection, daily as available** (date, time of blood draw; Complete Blood Count (CBC), serum creatinine, aspartate aminotransferase (AST), alanine transaminase (ALT) and serum total bilirubin, C-reactive Protein (CRP), lactate, # of blood cultures taken per patient, blood and sputum culture results (date/time, infecting pathogen), urine legionella and/or urine pneumococcus (if available), Procalcitonin (PCT))
- **Antibiotic Therapy** (agent, dosing, date and time at start and stop). More specifically, each agent will be documented daily as being started, continued or stopped including date and time of start and stop.
- **Antibiotic Therapy Decision Rationale at start/stop** (reasons for starting, stopping and/or not starting new therapy (drop down: PCT Algorithm + clinical status, improving clinical status, worsening signs and symptoms, clinical assessment did not match PCT algorithm, other (free text))).
- **Presence of pre-defined overruling criteria** (indicated according to Appendix A, 11.2)
- **Reason if recommendation from stewardship team is overruled** (Clinician gave antibiotics before recommendation was available; Clinician believes bacterial infection present; Clinician unfamiliar/uncomfortable/disagrees with PCT value; Attending physician overruled; Patient 's clinical condition is worsening/severely ill; Borderline PCT result; Patient expectations/satisfaction required antibiotics; COPD exacerbation/flare for anti-inflammatory properties (particularly for azithromycin); Meets guideline criteria for ABX in COPD flare; Other, free text))
- **Antibiograms** – antibiotic susceptibility will be collected to determine evolution of multi-drug resistant flora.
- **Secondary infections** – microbiological evidence of secondary infection will be captured to monitor patients throughout the patient's hospitalization
- **Concomitant Therapy** - (list of current medications)
- **Azithromycin** (query at time of randomization and on study day 5 if used for non-antibiotic purposes according to Appendix G)
- **Survival status** (at ICU discharge, hospital discharge, 30-days after discharge if available)
- **CDI status** occurs during hospitalization or is identified upon rehospitalization within 30 days after enrollment
- **Disposition** (date last follow up and disposition: dead, alive, unknown)
- **Complications until Day30** (Septic shock, mechanical ventilation, renal failure, lung abscess/empyema, development of pneumonia in non-pneumonia LRTI: date and time at start and stop)

7.2 Healthcare Resource Utilization Data

- **Cost of Antibiotics** (total cost of antibiotics per patient inclusive of antibiotic, tubing, IV bag, discharge antibiotic prescription)
- **Total per patient cost** (including blood cultures and mechanical ventilation days)
- **Antibiotic ADRs (e.g. CDI)**
- **AB days difference plus prescriptions avoided, and infection adverse event incidence modeling²⁹**
- **Cost of readmissions**
- **Cost of Procalcitonin**

8 STATISTICS

For more detailed information regarding the statistics portion, please refer to the Statistical Analysis Plan (SAP).

8.1 Study Design

8.1.1 Study type

Prospective randomized controlled two-arm multi-center trial, see Section 4.

8.1.2 Study goal

The study goal is to validate that a specified PCT algorithm applied to non-COVID-19 patients hospitalized with suspected pneumonia

1. reduces antibiotic exposure specified as an increase of *short* antibiotic pneumonia treatments lasting less than 4 days,
2. is not inferior concerning safety according to composite adverse events until day 30, and
3. reduces antibiotic exposure specified as a decrease of antibiotics prescribed at discharge for pneumonia treatment.

8.1.3 Randomization

Patients will be randomized with equal 50% probability to the two treatment arms “PCT arm” and “control arm”, see Section 6. Block randomization per study site will be applied, with random block length in order to prevent the possibility of predicting study arm assignments.

8.2 Mathematical Definitions

8.2.1 Short antibiotic treatments (“shortABx”, primary endpoint)

will be encoded as the proportion of patients per study arm (PCT arm, control arm) with less than 4 days of antibiotic duration

“antibiotic duration” (third secondary endpoint) is defined as the number of days per patient with antibiotic treatment for pneumonia comprising the number of days of antibiotic treatment during hospitalization (“ABx-days_{hospital}”), starting with the first day of PCT measurement which is one day

before enrollment into the study, counting all days with antibiotics not marked “not used for pneumonia”) and the number of prescribed days of antibiotic treatment at hospital discharge (“ABx-days_{prescribed at discharge}”, counting all days with antibiotics marked “to treat pneumonia”). The resulting sum will be bounded up to a maximum follow-up time of 30 days:

$$\text{Antibiotic duration} = \min(30, \text{ABx-days}_{\text{hospital}} + \text{ABx-days}_{\text{prescribed at discharge}})$$

8.2.2 The first secondary endpoint “**composite adverse events until day 30**” (“CAE30”) will be encoded as the patient level Boolean inclusive disjunction (“OR”) of the following eight binary (true/false) single adverse event endpoints (1a) all-cause in-hospital mortality, (1b) all-cause mortality after discharge (as available), (2) septic shock (vasopressor use for > 1 h), (3) mechanical ventilation (via endotracheal tube), (4) needed dialysis, (5) lung abscess/empyema or (6) hospital readmission.

The variable CAE30 mirrors the safety endpoint for pneumonia used in the study ProACT⁸. And, also as in ProACT, the endpoint will be analyzed in the form of study-arm-specific proportions, see Section 8.6.

8.2.3 The second secondary endpoint “**antibiotic exposure at discharge**” (“prescribedABx”) will be encoded as the proportion of patients per study arm (PCT arm, control arm) with antibiotic prescription for pneumonia treatment at discharge from index hospitalization.

8.2.4 The third secondary endpoint “**antibiotic duration**” will be computed per patient as described in Subsection 8.2.2.

8.2.5 The fourth secondary endpoint “**days of therapy per 1000 patient days**” will be computed per patient i as follows (i: index distinguishing different study patients):

$$\text{DoT}(\text{patient } i) = \text{antibiotic duration}(\text{patient } i) / \text{los30}(\text{patient } i) \times 1000$$

with length of stay of patient i

8.2.11 Exploratory Endpoints

All the individual variables constituting the composite safety endpoint “composite adverse events until day 30” will be considered as exploratory endpoints and be encoded in Boolean-binary form (true/false).

8.3 Primary Study Hypothesis

For the primary study endpoint “**short antibiotic treatments**” (“shortABx”; proportion of patients with short antibiotic treatments of pneumonia less than 4 days) the study hypotheses for statistical inference are as follows:

H0: The probability of patients with short antibiotic treatment of pneumonia is smaller or equal in the PCT arm versus the control arm.

H1: The probability of patients with short antibiotic treatment of pneumonia is greater in the PCT arm than in the control arm.

Note that the study goal is one-sided: to validate a shortABx probability in the PCT arm that is higher than the shortABx probability in the control arm (see Section 8.6 and 8.9; one-sided statistical testing at 2.5% significance level controlled for multiple testing / interim analyses. Bayesian statistics with uninformative priors will be applied for analysis (see Section 8.6.2).

8.4 Analysis Populations

The intention-to-treat (“**ITT**”) patient population will comprise all randomized non-COVID-19 patients.

The per-protocol (“**PP**”) patient population will comprise all ITT patients

- (a) fulfilling study inclusion criteria,
- (b) not meeting study exclusion criteria at enrollment,
- (c) even if meeting study exclusion criterion after enrollment or meeting a pre-defined overruling criterion,

- (d) with PCT measurements performed daily in the first week and thereafter at least every 48 hours during hospitalization and antibiotic treatment,
- (e) if assigned to PCT group, antibiotic steward ship team recommendation given to the treating physician on enrollment day and for each PCT measurement taken Monday-Friday described under d) and antibiotics stopped according to the PCT algorithm. An exception will be made if the stewardship team decides the patient will be given the same recommendation throughout their hospitalization.

Consequently, it should be noted that stewardship team recommendations should also be provided for patients meeting pre-defined overruling criteria (e.g., need for ICU care) since such patients may still qualify for the per-protocol population.

Patients of the PCT arm who are discharged before that day's PCT has resulted will be excluded from the per protocol population. Patients in the PCT arm who were continued on antibiotics despite a weekend/holiday/no stewardship team member available PCT value that would have resulted in an stewardship team recommendation to stop antibiotics will also be excluded from the per protocol population. Patients in the PCT arm whose antibiotics were discontinued despite weekend/holiday/no stewardship team member available PCT value that would have resulted in continuation of antibiotics will also be excluded.

- (f) if assigned to control group, no PCT measurements to treating physician during index hospitalization.

Primary analysis of the superiority endpoint “antibiotic exposure” will be conducted on the basis of the ITT patient population. Analysis of the non-inferiority endpoint “composite adverse events until day 30” will be conducted on the basis of PP and ITT patient population. PP-results will be compared and discussed with corresponding results obtained for ITT patient population.

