1.6 Study Plan

	Between presentation and enrollment day	Screening/ Enrollment day	Per Protocol until discharge (as available)	Hospital Discharge	Day 30
Medical History	x				
Routine Clinical Assessment	x	x	x		
Standard laboratory evaluation	x	x	x		
Inclusion/Exclusion		x			
PCT measurement	x	x	x*		
Document presence or absence of safety endpoints and antibiotic prescription				x	x
Follow-up via chart review/public record: readmission, survival status					x
Follow-up via chart review: Readmission for CDI					x

*PCT measurement only until antibiotics are stopped or patient becomes ineligible

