Upon randomization, the research staff will send a welcome message to both the standard of care and intervention teams. Enrollment PCT values consist of one value from the day of randomization (D1) and one value from a previous day 6-48 hours prior (D0). All PCT measurements throughout the study should be obtained using discarded blood from routine lab work. All PCT values ordered by the study team for patients in the intervention arm will be released in EPIC, while those of the standard of care arm will be suppressed.

After the PCT results are available, the stewardship team will review both the D0 and D1 results as a pair and provide an antibiotic recommendation (PCT intervention arm only) using the stewardship team recommendation template to the primary provider service on enrollment day. If the stewardship team is discordant with the PCT algorithm (see section 1.5 for algorithm), they will be sent a discordance survey (see Appendix G). If the primary team is discordant with the stewardship recommendations, a reason for discordance survey will be sent out and recorded in REDCap (see Appendix H). Patient information will be recorded in REDCap for both the intervention and standard of care arms.

(D2+) Daily PCT measurements

For patients who are still eligible and on antibiotics, PCT should be measured daily for one week and then Monday, Wednesday, and Friday in both arms. If there are no results on a Monday, the PCT will be measured on Tuesday, Wednesday, and Friday. If there are no results on a Wednesday, the PCT will be measured on Monday, Thursday, and Friday.

For PCT arm patients, the stewardship team will review available PCT results and provide an antibiotic recommendation to the primary provider service on the same calendar day. Antibiotic monitoring and/or discontinuation will be guided by clinical assessment (medical history, physical exam, imaging and standard laboratory evaluations) as well as the PCT algorithm (Appendix A, LRTI) and pre-defined overruling criteria (Appendix A, 11.2). If the stewardship team is discordant with the PCT algorithm, a discordance survey will be requested (Appendix G). In case of discordance between the primary team and the stewardship team, a discordance survey will also be requested (Appendix H).

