3.1 Analysis Populations

The intention-to-treat (“ITT”) patient population will comprise all randomized non-COVID-19 patients. The per-protocol (“PP”) patient population will comprise all ITT patients (a) fulfilling study inclusion criteria, (b) not meeting study exclusion criteria at enrollment, (c) even if meeting study exclusion criterion after enrollment or meeting a pre-defined overruling criterion, (d) with PCT measurements performed daily in the first week and thereafter at least every 48 hours during antibiotic treatment, (e) ~~-if assigned to PCT group, antibiotic steward~~ ship team recommendation given to the treating physician on enrollment day and for each PCT measurement taken Monday-Friday described under d) and antibiotics stopped according to the PCT algorithm. An exception will be made if the ASP decides the patient will be given the same recommendation throughout their hospitalization.

Consequently, it should be noted that ASP recommendations should also be provided for patients meeting pre-defined overruling criteria (e.g., need for ICU care) since such patients may still qualify for the per-protocol population.

Patients of the PCT arm who are discharged before that day’s PCT has resulted will be excluded from the per protocol population. Patients in the PCT arm who were continued on antibiotics despite a weekend/holiday/no ASP member available PCT value that would have resulted in an ASP recommendation to stop antibiotics will also be excluded from the per protocol population. Patients in the PCT arm whose antibiotics were discontinued despite weekend/holiday/no ASP member available PCT value that would have resulted in continuation of antibiotics will also be excluded.

(f) if assigned to control group, no PCT measurements to treating physician during index hospitalization.

Primary analysis of the superiority endpoint “antibiotic exposure” will be conducted on the basis of the ITT patient population. Analysis of the non-inferiority endpoint “composite adverse events until

day 30" will be conducted on the basis of PP and ITT patient population. PP-results will be compared and discussed with corresponding results obtained for ITT patient population.

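### Per-protocol criterion (d) does not match the protocol's own PCT sampling plan, so a patient managed to plan can drop out of the set on which CAE30 non-inferiority is tested

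*Protocol*

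**What the plan says.** Criterion (d) in Protocol 8.4 keeps patients "with PCT measurements performed daily in the first week and thereafter at least every 48 hours during hospitalization and antibiotic treatment". SAP 3.1 reads "with PCT measurements performed daily in the first week and thereafter at least every 48 hours during antibiotic treatment", without the reference to hospitalization. Both apply to both arms and make no exception for a day without blood.

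The sampling plan is set elsewhere in the protocol:

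- **Source of blood (4.1):** "All PCT measurements throughout the study should be obtained using discarded blood from routine lab work".
- **Frequency (4.1):** "PCT should be measured daily for one week and then Monday, Wednesday, and Friday in both arms", for patients still eligible and on antibiotics.
- **Fallback (4.1):** "If there are no results on a Monday, the PCT will be measured on Tuesday, Wednesday, and Friday". A similar shift covers a missing Wednesday. Week 1 has no fallback.
- **Availability:** the post-enrollment in-hospital column of the study plan (1.6) is qualified by availability. Section 7.1 lists PCT under "Laboratory Values included in the standard care of a patient hospitalized with suspected infection, daily as available".
- **Guaranteed samples (4.2.1):** two, which 4.1 calls D0 and D1.

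Protocol 8.6.3 and SAP 4.5 base the CAE30 non-inferiority analysis on PP, with ITT also run and compared. SAP 2.3.3 and Table 2.6 use PP for CAE30 in the testing hierarchy and in the power figures.

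**The concern.** A per-protocol set should screen out departures from the protocol. Here the site may use only leftover blood, so on a day with no routine draw there can be no PCT value and nobody has broken a rule. Criterion (d) still fails the patient. In the control arm the result is blinded and cannot alter care, so a missing value there says nothing about the treatment received.

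Membership under (d) then depends on how often clinicians order blood and on how many inpatient days the patient spends on antibiotics. Both arise after randomisation, and the second is what the intervention aims to shorten. That is not the random 50% subset of SAP 2.3.3. At stake are the composition and size of the set behind the CAE30 claim. That claim also gates the prescribedABx test in the hierarchy of SAP 2.4.

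**Working it through.** **1. The SAP's power figure.** Inputs from SAP 2.3.3 and Table 2.6: 20% marginal CAE30 rate, RR 0.9, margin 10 points, γ = 0.985, 350 PP patients (175 per arm).

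- p_ctrl = 2 × 0.20 / 1.9 = 0.2105; p_PCT = 0.9 × 0.2105 = 0.1895.
- SE = √[(0.2105 × 0.7895 + 0.1895 × 0.8105) / 175] = 0.0427.
- (0.10 + 0.0211) / 0.0427 = 2.83. Subtracting z(0.985) = 2.17 leaves 0.66, so power is about 74.6%.
- Exact enumeration with Beta(1,1) priors gives 74.9%, or 74.1% after multiplying by the 99% shortABx power. Interim stopping was not simulated.

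The stated 75% reproduces. The same calculation, with the 99% factor, gives 64% at a 40% PP share and 83.5% at 63%. The PP share therefore matters, but the documents do not say how much of the loss comes from (d).

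**2. The schedule against the 48-hour rule.** Friday to Monday is 3 × 24 = 72 hours. With the Monday fallback, Friday to Tuesday is 96 hours. With the Wednesday fallback, Monday to Thursday is 72 hours. A patient still in hospital on antibiotics after week 1 therefore fails the 48-hour rule over the first on-schedule weekend, with no missed draw.

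**3. Week 1.** D0 and D1 are guaranteed by inclusion, and antibiotic duration is counted from D0 (Protocol 8.2.1). Days at risk of a gap are therefore at most course length minus 2. If u is the chance that an inpatient antibiotic day has no routine draw, taken as independent between days, the chance of passing is (1 − u)^(days at risk). The range u = 5% to 20% is assumed.

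| Days on antibiotics in hospital, from D0 | Days at risk | Pass at u = 5% | Pass at u = 20% |
|---|---|---|---|
| 3 | 1 | 95% | 80% |
| 5 | 3 | 86% | 51% |
| 7 | 5 | 77% | 33% |

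**4. Direction of selection.** This is an illustration with no true effect on CAE30 and all inputs assumed. One third of patients are severe, with event rates of 36% severe and 12% mild (20% overall). Control courses are 4 days (mild) and 6 days (severe), and u is equal in all patients. The retained severe-to-mild ratio is 0.5 × (1 − u)^(severe days − mild days), so the two guaranteed days cancel. The PP event rate is 0.12 + 0.24 × the severe share.

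| PCT-arm courses (mild, severe) | PP difference, PCT − control, u = 5% | u = 10% |
|---|---|---|
| 3, 6 (only mild shorten) | −0.3 points | −0.5 points |
| 3, 5 (both shorten by 1) | 0.0 | 0.0 |
| 3, 4 (severe shorten more) | +0.3 points | +0.5 points |

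At u = 5%, the control ratio is 0.5 × 0.95² = 0.451, the severe share 0.311 and the rate 19.46%. In the first row the PCT ratio is 0.5 × 0.95³ = 0.429, the share 0.300 and the rate 19.20%. The sign depends on whose courses shorten, which the documents do not state.

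**5. Pilot retention (Protocol Table 8.1).** PP/ITT was 30/48 = 62.5% in the PCT arm and 30/47 = 63.8% in control.

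**The case against.** Protocol 5.1 presumes that routine sampling is daily in every study patient, and (d) mirrors the week-1 frequency in 4.1. A missed day could be called a schedule departure, and the availability wording in 1.6 heads a whole column rather than waiving PCT. This has some force for week 1, but presuming a daily draw is not requiring one. It does not answer the weekend gap, where a fully on-schedule patient fails.

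ITT is also analysed and compared, so a discrepancy between the sets could be seen. That stands as a safeguard, though PP remains the stated basis in the hierarchy. The 75% power already allows for a 50% PP share estimated from the running study. That also stands, so no power gain can be promised from a wider (d).

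A reader might go further and infer that (d) removes more control patients and so favours a non-inferiority claim. For (d) alone, with equal draw frequency in both arms, control does lose slightly more: 0.2 to 5.3 points for a daily draw probability of 0.99 down to 0.80. That calculation used pilot shortABx rates, stays simulated at the SAP's rate of 0.12 (read as per day), and assumed courses of 3 days if short and 5 or 7 otherwise. The documents do not support the wider inference. They report no draw rates and no exclusions by criterion. Pilot retention was nearly equal, and criterion (e) with its discharge and weekend rules removes PCT-arm patients only. The bias can also vanish or reverse, as the illustration shows. Equal pilot totals do not prove (d) neutral either, because they pool all criteria and may hide different kinds of patient.

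**Conclusion.** The mismatch is in the text and rests on no assumption. Criterion (d) demands more than the sampling plan can guarantee in week 1, and more than the plan schedules afterwards. Read literally, it excludes patients managed to plan from the set carrying the CAE30 non-inferiority test, by a mechanism the SAP's random-subset simulation does not represent.

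The size is not known. The week-1 loss depends on an assumed no-draw rate: 86% to 51% of 5-day courses would pass (d) at 5% to 20% no-draw days. The direction of any between-arm bias is undetermined, and neither a control-arm excess nor a tilt towards non-inferiority should be claimed. The point merits correction because the rule is avoidable and cheap to repair.

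**What to change.** In Protocol 8.4(d) and SAP 3.1(d), identically for both arms, state: *PCT measured on every day scheduled in section 4.1 on which a routine blood sample was available, during hospitalization and antibiotic treatment; a day without a routine draw is not a deviation.* Replace the 48-hour wording with the section 4.1 schedule. This also restores the in-hospital limit missing from the SAP; without it, (d) read literally extends to antibiotics taken after discharge. It also settles patients who become ineligible: their PCT measurement stops under 6.2, while criterion (c) keeps them in PP.

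Tabulate PP exclusions by criterion and arm beside the ITT CAE30 result, so that any imbalance is visible.

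Do not drop (d) for the control arm only. That would give the arms different PP rules and create a between-arm selection of its own.

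The cost is wording in two documents, one derivation from laboratory dates already in the eCRF, and one table. Sampling and patient care do not change. The downside is small: some PCT-arm patients with fewer PCT-guided days stay in PP, and their number can be reported.
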